## 1. Background/introduction

DOTAREM® (Gd-DOTA) is a paramagnetic contrast agent for Magnetic Resonance Imaging (MRI) which has been marketed in numerous countries worldwide since 1989. In this molecule, Gadolinium is tightly bound to the DOTA ligand and becomes inaccessible to the external medium so that only its paramagnetic effect can be expressed. Numerous clinical trials have been performed with DOTAREM® to evaluate its tolerance and diagnostic contribution. The product is registered and marketed for various indications including neurological, whole body and angiographic indications.

The usual dose of DOTAREM® for these examinations is 0.1 mmol/kg but a dose up to 0.3 mmol/kg is recommended for some brain-imaging indications. The recommended dose is 0.1 mmol/kg i.e. 0.2 ml/kg in adults, children and infants. In angiography, depending on the results of the examination being performed, a second injection may be administered during the same session if necessary. In some exceptional cases, as in the confirmation of isolated metastasis or the detection of leptomeningeal tumours, a second injection of 0.2 mmol/kg can be administered.

Despite the possible interest of plain Magnetic Resonance (MR) examinations in some pathologic circumstances, Gadolinium based products like DOTAREM® have widely demonstrated their superiority over plain MRI and also over other imaging modalities in numerous pathologies.

As of today, based on post-marketing surveillance, more than 15 million units of DOTAREM® have been dispensed. To date, irrespective of the dose, adverse events reported in clinical trials, as well as those spontaneously reported, consist of paresthesia, headaches, sensation of heat, cold and/or pain at the injection site, nausea, vomiting and skin reactions such as erythema, rash and pruritus. Rare anaphylactoid reactions have been reported. A recent post-marketing study involving more than 24.000 patients has provided the largest analysis of tolerance, adverse reactions and diagnostic yield with the use of DOTAREM® since its introduction into clinical practice. AEs were noted in only 0.4% of the examinations and were mostly rated as minor.

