5.4. Demographic and Other Baseline Characteristics

All demographic variables and other baseline characteristics will be presented using the SP. Demographics variables will be presented using the AIP as well.

Demography

Summary statistics for quantitative variable will be calculated for age, body weight, height and BMI. Frequency and percentages will be calculated for gender.

BMI will be derived for each collection of body weight using the formula: $BMI = \frac{\text{BodyWeight_Kg}}{\text{Height_m}^2}$

Magnetic Field

Summary statistics for qualitative variable will be presented for magnetic field (in tesla).

Current renal status

Summary statistics for quantitative variable will be calculated for serum creatinine, estimated creatinine clearance and eGFR. Frequency and percentages will be calculated for current renal status.

Serum creatinine will be presented in $\mu\text{mol/L}$. Therefore, conversion will apply for measurement in mg/L and mg/dL using the following conversion factors [1]:

From mg/dL to $\mu\text{mol/L}$: multiply by 88.4

From mg/L to $\mu\text{mol/L}$: multiply by 8.84

Should be noted that an aberrant result of serum creatinine was entered in the database for one patient ($1.36 \mu\text{mol/L}$). As it was impossible to correct this discrepancy in the database, it was decided not to present it in the statistical results of the clinical study report.

CONFIDENTIAL	FORM STATISTICAL ANALYSIS PLAN N° DGD-55-003 VERSION N° 2 (REF I011622)	F015830-01 Page 16 / 49
--------------	--	----------------------------

The estimated creatinine clearance (mL/min) will be calculated using the Schwartz formula for children less than 2 years old. The eGFR (mL/min/1.73 m²) will be calculated using the MDRD formula otherwise. They will be presented independently.

Risk factors

Frequency and percentages will be calculated for each risk factor. Specification for other cardiovascular disease, nervous system disorders, other treatments at risk and dose of Erythropoietin will be only listed.

Previous examination with GBCA

Number of patients with at least one previous examination with GBCA will be displayed globally and by classified name of product. Name of product will be classified as the following:

- If the words “Gadovist” or “Gadavist” appear in the product name then class= “Gadobutrol”
- If the word “Dotarem” appears in the product name then class= “Gadoterate meglumine”

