- If the word “Primovist” or “Gd-EOB-DTPA” or “Gd EOB” appear in the product name then class= “Gadotexate disodium”
- If the words “Magnevist” or “Gadopentetate” appear in the product name then class= “Gadopentetate dimeglumine”
- If the word “Multihance” appears in the product name then class= “Gadobenic acid meglumine”
- If the word “Omniscan” appears in the product name then class= “Gadodiamide”
- If the word “Optimark” appears in the product name then class= “Gadoversetamide”
- If the words “No contrast” or “without contrast” or “NA” or “Non-contrast brain MRI” appear in the product name then class = “Without Contrast”
- If the words “Unknown” or “MD” or “UN” or nothing appear in the product name then class = “Missing”
- Otherwise then class= “Other”

Recent surgeries

Surgeries done less than two years before the MRI examination with DOTAREM® will be only listed. Number of patients with at least one surgery will be tabulated.

Concomitant treatments

Concomitant treatments at the time of the MRI examination with DOTAREM® will only be listed. Number of patients with at least one concomitant medication will be tabulated.

Indication of MRI examination

Indication of MRI examination will be tabulated by main classification (Central nervous system, whole body, musculoskeletal system, angiography and other) and sub classification.

Some indications for MRI categorized as “Other” should be classified in pre-defined categories according to the following algorithm:

If the wording contains “angio” or “anjio” then classify to Angiography system and according to the following for the sub classification:

If the wording is:	Specified Organ
“kidney” or “kidneys” or “renal” or contains one of these	2=Renal

CONFIDENTIAL	
FORM STATISTICAL ANALYSIS PLAN N° DGD-55-003 VERSION N° 2 DATED: 26 FEBRUARY 2018 (REF I011622)
	F015830-01 Page 17 / 49
--------------	---	----------------------------

“iliac” or contains “iliac”	3=Aorto iliac
“calf”	4=Calf
“Otherwise”	5=Other

Otherwise classify to whole body system and according to the following, for the sub classification:

If the wording is:	Specified Organ
“liver” or contains “lilver”	1=Liver
“kidney” or “kidneys” or “renal” or contains one of these	2=Kidney
“pancreas”	3=Pancreas
“pelvis” or contains “pelvic” or contains “pelvin”	4=Pelvis
“lung”	5=Lung
“heart” or “cardiac” or “cardio”	6=Heart
“breast”	7=Breast

Premedication

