5.6.6. Vital signs, physical findings and other observations related to safety

Medical events will be coded in body systems and preferred terms using MedDRA dictionary v16.0.

Medical Event overview

Number and percentage of patient having undergone medical events will be tabulated by follow-up visit

MRI examination

Number of patients with MRI examination will be displayed by follow-up visit and by name of product. Name of product will be coded using WHO DD 2015 version and will be tabulated according to ATC code.

Medical Event by SOC and PT

Medical events will be displayed by follow-up visit and by SOC and PT.

Listing of medical events will be presented in CSR appendix 16.2.9.

CONFIDENTIAL	FORM STATISTICAL ANALYSIS PLAN N° DGD-55-003 VERSION N° 2 DATED: 26 FEBRUARY 2018 (REF I011622)	F015830-01 Page 20 / 49
--------------	---	----------------------------

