eGFR (mL/min/1.73 m ²) for Patients Older than 2 Years Old		xxx (xx.x%)
If Yes, eGFR	n	xx
	Mean (SD)	xx.xx (xx.xx)
	Median	xx.x
	Min ; Max	xx.x ; xx.x
	Missing (if applicable)	xx

eGFR: Estimated Glomerular Filtration Rate.

SD: Standard Deviation.

%: (n row / n non missing) * 100, except for Estimated Creatinine Clearance and eGFR variables %: (n row / N safety population) * 100.

Source: Listing 16.2.4.3.

CONFIDENTIAL	FORM STATISTICAL ANALYSIS PLAN N° DGD-55-003 VERSION N° 2 DATED: 26 FEBRUARY 2018 (REF I011622)	F015830-01 Page 31 / 49
--------------	---	----------------------------

Table 14.1.4.4 Pre-existing Risk Factor and Medical History - Safety Population

	Total (N=XXX)
Liver Disorder	xxx (xx.x%)
Allergies	xxx (xx.x%)
Previous Reaction to Contrast Agents	xxx (xx.x%)
GBCA	xxx (xx.x%)
Iodinated Contrast Agent	xxx (xx.x%)
Bronchial Asthma	xxx (xx.x%)
Hypertension	xxx (xx.x%)
Heart Insufficiency	xxx (xx.x%)
NYHA Class I	xxx (xx.x%)
NYHA Class II	xxx (xx.x%)
NYHA Class III	xxx (xx.x%)
NYHA Class IV	xxx (xx.x%)
Other Cardiovascular Disease	xxx (xx.x%)
Diabetes Mellitus	xxx (xx.x%)
Type I	xxx (xx.x%)
Type II	xxx (xx.x%)
Proteinuria	xxx (xx.x%)
Nervous System Disorders	xxx (xx.x%)
At Risk Treatments	xxx (xx.x%)
Beta-Blockers	xxx (xx.x%)
Interleukine2	xxx (xx.x%)
Other	xxx (xx.x%)
Hypothyroidism	xxx (xx.x%)
History of Deep Venous Thrombosis	xxx (xx.x%)
Erythropoietin	xxx (xx.x%)
Acidosis	xxx (xx.x%)
Hyperphosphatemia	xxx (xx.x%)
Abnormal Ca ⁺⁺ Level	xxx (xx.x%)
High Serum Ferritin Level	xxx (xx.x%)

GBCA: Gadolinium based Contrast Agent ; NYHA: New York Heart Classification.

%: (n row / N safety population) * 100.

Source: Listing 16.2.4.4.

Table 14.1.4.5 Previous Examinations with GBCA - Safety Population

	Total (N=XXX)
Previous Examination	n xxx
Yes	xxx (xx.x%)
No	xxx (xx.x%)

CONFIDENTIAL	FORM STATISTICAL ANALYSIS PLAN N° DGD-55-003 VERSION N° 2 DATED: 26 FEBRUARY 2018 (REF I011622)	F015830-01 Page 32 / 49
--------------	--	----------------------------

Total (N=XXX)		
	Missing (if applicable)	xx
If Yes*	Gadobutrol	xxx (xx.x%)
	Gadoterate Meglumine	xxx (xx.x%)

	Without Contrast	xxx (xx.x%)
	Missing	xxx (xx.x%)

GBCA: Gadolinium based Contrast Agent.

%: (n row / n non missing) * 100, except for multiple answers %: (n row / n with previous examination) * 100.

*As multiple examinations with various GBCA are possible, the sum of percentage could be greater than 100.

Source: Listing 16.2.4.5.

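### Table 14.1.4.5 can count patients whose only prior MRI was non-contrast as GBCA-exposed, and mostly brand-based name matching can blur the split by agent

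*SAP*

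**What the plan says.** SAP 5.4 sets the quantity to be reported: "Number of patients with at least one previous examination with GBCA will be displayed globally and by classified name of product". Recorded product names are sorted into seven agent classes by the words they contain. Most rules look for brand names only: "If the word “Dotarem” appears in the product name then class= “Gadoterate meglumine", "If the words “Gadovist” or “Gadavist” appear in the product name then class= “Gadobutrol" and "If the word “Omniscan” appears in the product name then class= “Gadodiamide". Two classes accept more than a brand: "If the words “Magnevist” or “Gadopentetate” appear in the product name then class= “Gadopentetate dimeglumine", and the Primovist class also takes Gd-EOB-DTPA and Gd EOB. Entries indicating no contrast get their own class, blank or unknown names become 'Missing', and anything unmatched becomes 'Other'.

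The shell of Table 14.1.4.5 (SAP 7.2) carries GBCA in its title, but its Yes/No row asks only about a previous examination. The 'If Yes' block lists the agents and then "Without Contrast" and 'Missing'. Its footnotes divide each class row by the number of patients with a previous examination and warn that the rows may add to more than 100%.

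MRI products used during follow-up are handled by another method in SAP 5.6.6: "Name of product will be coded using WHO DD 2015 version and will be tabulated according to ATC code".

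**The concern.** The text promises a count of patients previously exposed to a gadolinium agent; the shell counts patients with a previous examination, contrast-enhanced or not. No sentence moves a patient to 'No' when every recorded examination was non-contrast. The global count can then be too high and every agent percentage too low.

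The second weakness is in the split by agent. A rule that knows gadodiamide only as Omniscan, and the study drug only as Dotarem, puts the generic names into 'Other'. Protocol Section 1 cites gadodiamide as having the highest NSF incidence, around 3-4%, and itself calls the study drug Gd-DOTA. The split is therefore informative, and a Gd-DOTA record shown under 'Other' would look like a different agent. At stake is the accuracy of the planned baseline summary of earlier gadolinium exposure in a study whose primary question is NSF.

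**Working it through.** The plan gives no figure on this point, so there is none to reproduce.

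**1. What the shell counts.** Let N be the patients in the 'Yes' row, E those with at least one GBCA record, and w the share of N whose recorded examinations were all non-contrast. Ignoring unknown products, E = N(1 − w). SAP 5.4 promises E; the shell prints N, which exceeds E by the factor 1/(1 − w). Non-contrast-only patients add nothing to any agent row but stay in its denominator, so a class printed as p should read p/(1 − w).

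The documents do not give w. As an assumption only, with N = 100 and a class printed as 30.0%:

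| Assumed w | E | N/E | Class percentage on E |
|---|---|---|---|
| 2% | 98 | 1.02 | 30.6% |
| 5% | 95 | 1.05 | 31.6% |
| 10% | 90 | 1.11 | 33.3% |
| 20% | 80 | 1.25 | 37.5% |

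**2. Whether a reader can undo it.** The non-contrast row counts everyone with any non-contrast record, including patients who also had a GBCA. With N = 100 and 20 patients in that row, E could be 80 (none of the 20 had a GBCA) or as high as 100 (all did). Subtraction gives E only if the class rows add to exactly 100%, that is, if no patient is in two classes. The footnote anticipates that they may not.

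**3. Name matching.** The SAP 5.4 rules were applied in their listed order under three readings: case-sensitive substring, case-insensitive substring, and case-insensitive whole word. The results below are the same under all three unless stated.

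- Of the SAP's 7 agent class names entered as the product, 1 maps to itself (gadopentetate dimeglumine). The other 6 go to 'Other': gadobutrol, gadoterate meglumine, gadotexate disodium (the SAP's spelling), gadobenic acid meglumine, gadodiamide and gadoversetamide.
- Gd-DOTA goes to 'Other', while Gd-EOB-DTPA is classified.
- The entry 'non contrast' goes to 'Other'. 'Non-contrast abdominal MRI' does so under two readings; under the third it reaches the non-contrast class only because 'abdominal' contains the letters 'na'.
- Under the case-sensitive reading, DOTAREM in capitals goes to 'Other'. The sample rows of Listing 16.2.4.5 classify capitalised brand names correctly, so case-insensitive matching is presumably intended, but it is not stated.

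An agent sent to 'Other' still counts in the global total, so for agents this step affects the class rows only.

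**4. The follow-up table.** Table 14.3.5.2 also has a non-contrast row under 'If Yes'. There the question is whether any MRI was done, so the row is consistent. In the baseline table, which is about GBCA, it is not. Adopting the follow-up coding would repair the names but not the denominator.

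**The case against.** The strongest reply is that nothing shows an actual misclassification. The SAP is dated February 2018, after recruitment stopped in March 2015, and SAP 5.4 discusses an individual creatinine value already in the database. Its string list includes entries as particular as 'Non-contrast brain MRI', 'MD' and 'UN'. The list may well have been written from the recorded names, in which case generic names are missing from it because few or none were entered. This is an inference, but a reasonable one, and it limits the name-matching point. It also cuts the other way: a string that particular suggests that non-contrast records do exist.

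It can also be said that the matching rule does separate non-contrast examinations and that the table shows them openly. That is correct. The miscount comes from the 'Yes' level and the denominator, and a visible row corrects neither.

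A reader might infer three larger harms. The documents support none of them:

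- *Information needed for a suspected NSF case is lost.* Listing 16.2.4.5 gives the recorded product name, date and volume for each patient beside the class.
- *False eligibility deviations arise for a non-DOTAREM agent within 12 months.* SAP 5.2 does not say that this deviation is derived from the class; deviations are sought in the database and monitoring files and can be added at the data review meeting. None leads to exclusion.
- *The NSF result is affected.* SAP 5.6.2 does not use the class, and the SAP plans no tests, covariates or subgroups.

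**Conclusion.** The point holds as a defect in one descriptive baseline table. Followed as written, the shell can overstate the number of patients with prior GBCA exposure and understate each agent's percentage. The literal name rule can also misstate the split by agent. The first effect requires patients recorded as 'Yes' whose examinations were all non-contrast, which the rule's own strings make likely. The second requires sites to have typed names the rule does not list, which is unknown.

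The size cannot be computed from the documents. The factors of 1.02 to 1.25 rest entirely on an assumed share of 2% to 20%. It would go too far to say that the recorded exposure history is wrong: the raw names are kept, the class does not enter the primary analysis, and both problems can be corrected from existing data.

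**What to change.** In SAP 5.4 and Table 14.1.4.5:

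- Define previous examination with GBCA as 'Yes' when at least one record has a class that is neither non-contrast nor missing, and use that count as the denominator for the product classes.
- Move patients with only non-contrast examinations, and patients whose product is unknown, to separate rows outside 'If Yes'. An unknown product may still have been a GBCA, so showing that group separately lets the reader see how far the count could rise.
- Match brand name, generic name and abbreviation for every agent, including gadodiamide, gadoterate and Gd-DOTA, or use the WHO DD coding already planned for follow-up. The coding alone is not enough; the change of denominator is needed as well.
- Cover common non-contrast spellings and state the case and whole-word rules. Under the new definition, a non-contrast entry left in 'Other' would count as exposure.
- Review the raw names that end in 'Other' before the table is finalised.

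The cost is a few lines of programming and SAP wording. No new data are needed.

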1.1. Study objectives

The primary objective of this study is to prospectively estimate the incidence of NSF in patients with moderate to severe renal impairment after administration of DOTAREM®. Patients will be followed during a two-year period after administration of DOTAREM®, to assess if signs or symptoms suggestive of NSF have appeared.

The secondary objectives of the study are:

- to collect a large number of data concerning the general safety profile of DOTAREM® during patient inclusion and MR examination,
- to collect information regarding MRI indication,
- to collect conditions of use/administration of the product in this specific population of patients,
- to collect efficacy data (image and diagnostic quality).

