Table 14.1.4.6 Recent Surgery - Safety Population

Total (N=XXX)		
At Least One Recent Surgery	n	xxx
	Yes	xxx (xx.x%)
	No	xxx (xx.x%)
	Missing (if applicable)	xx

%: (n row / n non missing) * 100.

Source: Listing 16.2.4.6.

Table 14.1.4.7 Concomitant Medications - Safety Population

Total (N=XXX)		
At Least One Concomitant Medication	n	xxx
	Yes	xxx (xx.x%)
	No	xxx (xx.x%)
	Missing (if applicable)	xx

%: (n row / n non missing) * 100.

Source: Listing 16.2.4.7.

Table 14.1.4.8 Indication of MRI Examination - Safety Population

Total (N=XXX)		
Central Nervous System		xxx (xx.x%)
	Head/Neck	xxx (xx.x%)
	Brain	xxx (xx.x%)
	Spinal Cord	xxx (xx.x%)
Whole Body		xxx (xx.x%)
	Liver	xxx (xx.x%)
	Kidney	xxx (xx.x%)

CONFIDENTIAL	FORM STATISTICAL ANALYSIS PLAN N° DGD-55-003 VERSION N° 2 (REF I011622)	F015830-01 Page 33 / 49
--------------	--	----------------------------

		Total (N=XXX)
	Pancreas	xxx (xx.x%)
	Pelvis	xxx (xx.x%)
Other Cardiovascular Disease		xxx (xx.x%)
	Lung	xxx (xx.x%)
	Heart	xxx (xx.x%)
	Breast	xxx (xx.x%)
Musculoskeletal System		xxx (xx.x%)
	Bones/Joints	xxx (xx.x%)
	Soft Tissue	xxx (xx.x%)
Angiography		xxx (xx.x%)
	Carotids	xxx (xx.x%)
	Renal	xxx (xx.x%)
	Aorto Iliac	xxx (xx.x%)
	Calf	xxx (xx.x%)
	Other	xxx (xx.x%)
Other		xxx (xx.x%)

MRI: Magnetic Resonance Imaging.

%: (n row / N safety population) * 100.

Source: Listing 16.2.4.8.

Table 14.1.4.9 Premedications - Safety Population

		Total (N=XXX)
At Least One Premedication	n	xxx
	Yes	xxx (xx.x%)
	No	xxx (xx.x%)
	Missing (if applicable)	xx

%: (n row / n non missing) * 100.

Source: Listing 16.2.4.9.

Table 14.2.2.1 Overall Quality of Images - Efficacy Population

		Total (N=XXX)
Image Quality	n	xxx
	Very Good	xxx (xx.x%)
	Good	xxx (xx.x%)
	Fair	xxx (xx.x%)
	Poor	xxx (xx.x%)
	Very Poor	xxx (xx.x%)
	Missing (if applicable)	xx

%: (n row / n non missing) * 100.

CONFIDENTIAL	FORM STATISTICAL ANALYSIS PLAN N° DGD-55-003 VERSION N° 2 DATED: 26 FEBRUARY 2018 (REF I011622)	F015830-01 Page 34 / 49
--------------	--	----------------------------

Source: Listing 16.2.6.1.

Table 14.2.2.2 Diagnostic Quality - Efficacy Population

		Total (N=XXX)
Diagnosis	n	xxx
	Yes	xxx (xx.x%)
	No	xxx (xx.x%)
	Missing (if applicable)	xx
If No, Reason*		
	Technical Problem	xxx (xx.x%)
	Anxious Patient	xxx (xx.x%)
	Other	xxx (xx.x%)

%: (n row / n non missing) * 100, except for multiple answers %: (n row / n with no diagnosis) * 100.

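### Read literally, the SAP 5.4 rule sends every recoded 'Other' MRI indication without 'angio' or 'anjio' to whole body, and the Table 14.1.4.8 shell puts lung, heart and breast under a risk-factor label

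*SAP*

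**What the plan says.** Describing MRI indication is a secondary objective; SAP 1.1 words it as "to collect information regarding MRI indication". The reporting plan is in SAP 5.4: "Indication of MRI examination will be tabulated by main classification (Central nervous system, whole body, musculoskeletal system, angiography and other) and sub classification". That gives five main classes.

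SAP 5.4 then adds a recoding step: "Some indications for MRI categorized as “Other” should be classified in pre-defined categories according to the following algorithm". It has two branches.

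- First branch: "If the wording contains “angio” or “anjio” then classify to Angiography system and according to the following for the sub classification". Its list covers renal, aorto-iliac, calf and a closing catch-all coded as other.
- Second branch: "Otherwise classify to whole body system and according to the following, for the sub classification". Its list runs from liver (code 1) to breast (code 7), with lung as 5 and heart as 6. It has no catch-all.

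The shell of Table 14.1.4.8 (SAP 7.2) shows the five classes plus a sixth row at the same level, "Other Cardiovascular Disease". This row stands between the pelvis and lung rows, and lung, heart and breast follow it as sub-rows. Percentages use the whole safety population as denominator.

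**The concern.** A recoding rule should be able to reach every class in the table and should say what happens to text that matches nothing. This one reaches two of the five classes, and its second branch is unconditional. Free text naming the brain, the spine or a joint would be counted as whole body, and the shell has no whole-body row for entries without an organ.

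The shell raises a separate problem. It gives three organs a heading that SAP 5.4 does not define as an indication class. The same label is a risk-factor item in the SAP 5.4 text and in the Table 14.1.4.4 shell.

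At stake is the only summary table for a stated secondary objective. Two programmers following SAP 5.4 could produce different versions of it.

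**Working it through.** The plan states no figure that depends on this rule, so there is nothing to reproduce. The check has three parts.

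**1. Trace the rule literally.** The wordings below are invented tests, not trial data. 'Contains' is applied only where SAP 5.4 says so; otherwise the wording must equal the listed term.

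| Wording entered under 'Other' | Main class | Sub-class |
|---|---|---|
| angio renal | Angiography | Renal |
| anjio iliac | Angiography | Aorto-iliac |
| angio calf | Angiography | Other |
| calf | Whole body | none |
| carotids mra | Whole body | none |
| kidney | Whole body | Kidney |
| pelvic mass | Whole body | Pelvis |
| heart | Whole body | Heart |
| liver | Whole body | Liver |
| liver mri | Whole body | none |
| pancreas mri | Whole body | none |
| brain, spine, knee | Whole body | none |
| abdomen | Whole body | none |

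Three things follow.

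- No path leads to central nervous system, to musculoskeletal system, or back to 'Other'.
- The calf row cannot be reached. It needs wording equal to 'calf', but its branch admits only wording that contains 'angio' or 'anjio'.
- The liver row's 'contains' term is spelt 'lilver', so a longer phrase with the correct spelling is not matched.

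By contrast, the angiography list and the contrast-product rule in the same section both end with a residual category.

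**2. Set the text beside the shell.**

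| Item | SAP 5.4 | Table 14.1.4.8 shell |
|---|---|---|
| Main-level rows | 5 | 6 |
| Lung, heart, breast | Whole body, codes 5 to 7 | Under "Other Cardiovascular Disease" |
| Residual whole-body sub-class | None | None |

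Moving the three organs under Whole Body would not change their own row counts. Whether the Whole Body total would change depends on how the program sums it, which the SAP does not say.

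**3. Bound the possible shift.** Let s be the share of the safety population with a recoded 'Other' entry, and u the share of those sent to whole body with no organ match. Percentage points moved = 100 × s × u. The documents give neither s nor u, so both are assumptions.

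| s | u = 25% | u = 50% | u = 100% |
|---|---|---|---|
| 1% | 0.25 | 0.5 | 1.0 |
| 5% | 1.25 | 2.5 | 5.0 |
| 10% | 2.5 | 5.0 | 10.0 |
| 20% | 5.0 | 10.0 | 20.0 |

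**The case against.** The best defence rests on scope. SAP 5.4 says that only some 'Other' entries are recoded, and both the class list and the shell keep an 'Other' class. That fits a rule meant only for entries naming a listed organ. This stands to the extent that misclassification is possible rather than certain. But the SAP gives no criterion for choosing the entries, and the second branch carries no condition. Under the narrow reading, central nervous system and musculoskeletal wording stays in 'Other' while angiography and whole-body wording is moved out, so it is not recovered on either reading.

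The matching terms may also be shorthand rather than code. The SAP is dated February 2018, after recruitment stopped in March 2015, and it records decisions taken on entered data. 'Anjio' and 'pelvin' look like spellings met in real entries, and 'lilver' may be another; this is inference. The point stands against simply deleting 'lilver'. It does not explain why the correct spelling has no 'contains' match.

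The shell heading is probably a label carried over from the risk-factor table. A fault in reading the table cannot be fully excluded, since a page break falls two rows above it. The organs still print under their own names.

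A reader might infer that the rule understates central nervous system and musculoskeletal use by taking patients out of those classes. The documents do not support this. Only entries already recorded as 'Other' are touched, and the shell has rows for head/neck, brain, spinal cord, bones/joints and soft tissue. Nothing shows that such scans were entered as 'Other'.

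A reader might also infer that the interpretation of dose is distorted, because Protocol section 1 notes that "a dose up to 0.3 mmol/kg is recommended for some brain-imaging indications". No planned analysis depends on that link: SAP 5.6.1 summarises exposure overall, SAP 3.11 plans no subgroups, and no table crosses dose with indication.

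**Conclusion.** The point holds as a defect of specification. Followed literally, the rule can inflate whole body at the expense of 'Other', leaves unmatched whole-body wording without a sub-class, and does not recover central nervous system or musculoskeletal wording entered as 'Other'. The shell contradicts SAP 5.4 on lung, heart and breast.

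It would go too far to say that the table will be wrong, or by how much. No count of 'Other' entries and no output is given. The span of 0.25 to 20 percentage points reflects assumed shares only. Entries first recorded in a pre-defined class are not recoded, although lung, heart and breast examinations meet the shell heading however they were entered.

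The effect is confined to one descriptive secondary table. Listing 16.2.4.8 shows classification, sub-classification and the specified text for each patient, so the coding can be checked. The NSF endpoint, the analysis populations and the sample size are not affected. The correction is still worth making, because it costs little.

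**What to change.** In SAP 5.4:

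- State which 'Other' entries are recoded.
- Recode to whole body only wording that names a listed organ.
- Add keywords for central nervous system (head/neck, brain, spinal cord) and musculoskeletal system (bones/joints, soft tissue).
- Leave unmatched wording in 'Other'.
- Use 'contains' matching throughout, which also makes the calf row reachable. Add 'liver', and keep 'lilver' if it occurs in the data.

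In the Table 14.1.4.8 shell, delete the "Other Cardiovascular Disease" row and place Lung, Heart and Breast under Whole Body.

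The cost is a change of SAP wording, a longer keyword list and one corrected shell. The free text is already collected, in the 'Specify' column of Listing 16.2.4.8.
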